4.2 Exclusion Criteria

Patients are not eligible for the trial if they fulfill any of the following exclusion criteria:

- All patients with active CNS involvement of lymphoma
- Prior organ transplantation, including allogeneic stem-cell transplantation
- Significant acute or chronic infections including, among others:
 - Known history of testing positive test for human immunodeficiency virus (HIV) or known acquired immunodeficiency syndrome (AIDS),
 - Hepatitis B virus (HBV) or hepatitis C virus (HCV) infection at screening (positive HBV surface antigen or HCV RNA if anti-HCV antibody screening test positive)
- Current use of immunosuppressive medication, EXCEPT for the following:
 - intranasal, inhaled, topical steroids, or local steroid injection (e.g., intra-articular injection); Systemic corticosteroids at a maximum dose of $\leq 1 \text{ mg/kg}$ of prednisone or

equivalent during screening (to be stopped by day 1 of trial treatment); Steroids as premedication for hypersensitivity reactions (e.g., CT scan premedication).

- Active autoimmune disease that might deteriorate when receiving an immunostimulatory agent. Patients with diabetes type I, vitiligo, psoriasis, hypo- or hyperthyroid disease not requiring immunosuppressive treatment are eligible
- Known prior severe hypersensitivity to investigational product or any component in its formulations, including known severe hypersensitivity reactions to monoclonal antibodies (NCI CTCAE v4.03 Grade ≥ 3)
- Persisting toxicity related to prior therapy of Grade >1 NCI-CTCAE v 4.03; however, alopecia and sensory neuropathy Grade ≤ 2 or other Grade ≤ 2 not constituting a safety risk based on investigator's judgment are acceptable
- Pregnancy or lactation
- Known alcohol or drug abuse
- Clinically significant (i.e., active) cardiovascular disease: cerebral vascular accident/stroke (< 6 months prior to registration), myocardial infarction (< 6 months prior to registration), unstable angina, congestive heart failure (\geq New York Heart Association Classification Class II), or serious cardiac arrhythmia requiring medication.
- Other severe acute or chronic medical conditions including colitis, inflammatory bowel disease, pneumonitis, pulmonary fibrosis or psychiatric conditions including recent (within the past year) or active suicidal ideation or behaviour; or laboratory abnormalities that may increase the risk associated with study participation or study treatment administration or may interfere with the interpretation of study results and, in the judgment of the investigator, would make the patient inappropriate for entry into this study
- Vaccination within 4 weeks of the first dose of avelumab and while on trial is prohibited except for administration of inactivated vaccines (e.g. the flu vaccine)
- Active infection requiring systemic therapy
- Major surgery within 4 weeks of trial entry
- Patients and partners of childbearing potential not willing to use two methods of effective contraception during and for 60 days after therapy

5. SCREENING AND CONSENT

5.1 Screening

The following assessments must be performed within 28 days prior to registration of a patient unless otherwise stated:

- Medical history – Including prior and current diagnosis,
- Physical Exam – Including vital signs (blood pressure, pulse and oxygen saturation), clinical disease assessment, ECOG assessment, height and weight
- Haematology – Full blood count (FBC) (Haemoglobin, Platelets, White Blood Count (WBC), Neutrophils and Lymphocytes)
- Blood Chemistry – Standard blood chemistry (to include bilirubin, AST/ALT, Alkaline, Calcium (adjusted), Creatinine, Creatinine Clearance, C-Reactive Protein, Magnesium, Potassium, Sodium, and glucose –non fasted) plus GGT, phosphate, triglycerides and, cholesterol
- Virology – HIV, HBV and HCV serology
- Pregnancy test - For female patients of childbearing potential, a serum pregnancy test, with sensitivity of at least 25 mIU/mL. Following a negative pregnancy result at screening, appropriate contraception must be commenced.
- Urinalysis – Protein, Glucose and Blood. If protein 2+ by semi-quantitative method (eg, urine dipstick), protein will have to be quantified by 24-hour urine collection and microscopic urinalyses will have to be done (Reflex Testing). If urine dipstick is positive for urine blood, microscopic urinalysis will have to be done (Reflex Testing)
- ECG - single 12 lead
- A bone marrow trephine biopsy (obtained within the last 3 months, however results are not required prior to trial entry) for relapsed and refractory patients

- Tissue biopsy (or bone marrow trephine if no other tissue available) to confirm relapse for all relapsed patients and to confirm refractory disease histology for refractory patients. These biopsies must have been obtained within the last 3 months. Sections will be collected for research and PD-L1 testing
- CT Scan (Neck, Chest, Abdomen and Pelvis)

For full details of the investigations see section 7.3

5.2 Informed Consent

It is the responsibility of the Investigator to obtain written informed consent for each patient prior to performing any trial related procedure. A Patient Information Sheet (PIS) is provided to facilitate this process. Investigators must ensure that they adequately explain the aim, trial treatment, anticipated benefits and potential hazards of taking part in the trial to the patient. The Investigator should also stress that the patient is completely free to refuse to take part or withdraw from the trial at any time. The patient should be given ample time (e.g. 24 hours) to read the PIS and to discuss their participation with others outside of the site research team. The patient must be given an opportunity to ask questions which should be answered to their satisfaction. The right of the patient to refuse to participate in the trial without giving a reason must be respected.

If the patient expresses an interest in participating in the trial they should be asked to sign and date the latest version of the Informed Consent Form (ICF). The Investigator must then sign and date the form. A copy of the ICF should be given to the patient, a copy should be filed in the hospital notes, and the original placed in the Investigator Site File (ISF). Once the patient is entered into the trial the patient's trial number should be entered on the ICF maintained in the ISF. In addition, if the patient has given explicit consent a copy of the signed ICF must be sent in the post to the Trials Office for review.

Details of the informed consent discussions should be recorded in the patient's medical notes, this should include date of, and information regarding, the initial discussion, the date consent was given, with the name of the trial and the version number of the PIS and ICF. Throughout the trial the patient should have the opportunity to ask questions about the trial and any new information that may be relevant to the patient's continued participation should be shared with them in a timely manner. On occasion it may be necessary to re-consent the patient in which case the process above should be followed and the patient's right to withdraw from the trial respected. Patients are permitted to re-consent at the same visit that new information is provided if they wish to do so.

Electronic copies of the PIS and ICF are available from the Trials Office and should be printed or photocopied onto the headed paper of the local institution.

Details of all patients approached about the trial should be recorded on the Patient Screening/Enrolment Log and with the patient's prior consent their General Practitioner (GP) should also be informed that they are taking part in the trial. A GP Letter is provided electronically for this purpose.

5.3 Contraception

The effects of the trial drug on the developing human foetus are unknown; thus, women of childbearing potential and men able to father a child must agree to use two methods of highly effective contraception throughout the study and continued for at least 60 days after the last dose or abstain from sex throughout the study period.

Highly effective methods of contraception are those that, alone or in combination, result in a failure rate of less than 1% per year when used consistently and correctly (ie, perfect use) and include the following:

1. Established use of oral, inserted, injected, implanted or transdermal hormonal methods of contraception is allowed provided the patient plans to remain on the same treatment throughout the entire study and has been using that hormonal contraceptive for an adequate period of time to ensure effectiveness.
2. Correctly placed copper containing intrauterine device (IUD).
3. Male sterilisation with absence of sperm in the post-vasectomy ejaculate.

4. Bilateral tubal ligation or bilateral salpingectomy or bilateral tubal occlusive procedure (provided that occlusion has been confirmed in accordance with the device's label).

5. Female partner who meets the criteria for non-childbearing potential, defined as:

- Have undergone a documented hysterectomy and/or bilateral oophorectomy;
- Have medically confirmed ovarian failure; or
- Achieved postmenopausal status, defined as follows: cessation of regular menses for at least 12 consecutive months with no alternative pathological or physiological cause. Status may be confirmed by having a serum follicle-stimulating hormone (FSH) level within the laboratory's reference range for postmenopausal women.

All sexually active male patients must agree to prevent potential transfer of and exposure to drug through semen to their partners by using a condom beginning with the first dose of investigational product and continuing for at least 60 days after the last dose.

6. TRIAL ENTRY

Patients will be registered to the trial via the Cancer Research UK Clinical Trials Unit (CRCTU) by phone or using the CRCTU systems portal. An eligibility checklist and registration form (found in the ISF) should be completed prior to registration by the Investigator or designee.

Registration via CRCTU systems portal:

<https://www.cancertrials.bham.ac.uk/AvailTLive>

Login details will be provided by the trials office as part of site initiation. The patient trial number will be provided by the online system. A report can be printed as confirmation.

Registration via [contact]

9am-5pm Monday to Friday

The patient trial number will be given over the telephone, followed by a fax confirmation.

7. TREATMENT DETAILS

7.1 Trial Treatment

All patients registered to the trial will receive avelumab at the dose of 10 mg/kg by intravenous (IV) infusion once every 2 weeks for 8 cycles (28 day cycles). Each infusion of avelumab should be delivered over 1h (-10/+20min) unless IRR is experienced (see Table 3). Avelumab dose should be prepared in accordance with the NHS England National Dose Banding Table for avelumab (please refer to the pharmacy manual)

All patients should be weighed within 3 days prior to day 1 dosing for every cycle to ensure they did not experience either a weight loss or gain >10% from the weight used for the last dose calculation. For weight change less than 10% the decision to recalculate the avelumab dose can be in accordance with institutional practice. If the patient experienced either a weight loss or gain >10% compared to the weight used for the last dose calculation, the amount of study drug must be recalculated.

Premedication

Premedication with an antihistamine and with paracetamol, to mitigate IRRs and is **mandatory** approximately 30 to 60 minutes prior to the first four doses of avelumab (Cycles 1-2), but may continue to be administered for subsequent cycles based upon clinical judgment and presence/severity of prior infusion reactions, at the treating Investigator's discretion. For example, 25-50 mg diphenhydramine and 500-650 mg paracetamol IV or oral equivalent should be considered.

This regimen may be modified based on local treatment standards and guidelines as appropriate provided it does not include systemic corticosteroids.

Avelumab should be administered in a setting that allows for immediate access to an intensive care unit or equivalent environment and administration of therapy for anaphylaxis, such as the ability to implement immediate resuscitation measures. Steroids (dexamethasone 10 mg), epinephrine (1:1,000 dilution), allergy medications (IV antihistamines), bronchodilators, or equivalents, and oxygen should be available for immediate access.

Following avelumab infusions, patients must be observed for 2 hours post-infusion for potential IRRs.

Patients will be assessed during the course of treatment, at progression or after completion of 8 cycles of treatment as described in section 7.3.

Avelumab will be supplied free of charge for trial patients by Pfizer. This IMP will be packaged and labelled in accordance with local regulations and Good Manufacturing Practice (GMP) by a third party contracted by the Sponsor. Site pharmacies will be required to add site specific details on receipt of avelumab.

Avelumab Solution for Infusion, 20 mg/mL is supplied as a clear, colourless non-pyrogenic solution, packaged in a Type I glass vial containing 10 mL of solution, with a rubber stopper, and aluminium overseal and flip off cap. Each single-use vial of MSB0010718C (avelumab) contains a sufficient amount of product to ensure an extractable volume of 10 mL (200 mg) at a concentration of 20 mg/mL formulated with a preservative-free acetate buffered solution at pH 5.2 in the presence of Polysorbate 20 and Mannitol.

The avelumab supplied will require further dilution prior to IV infusion. The investigational product will be administered intravenously according to the instructions provided in the AVAIL-T pharmacy manual. Unopened vials should be stored at 2-8°C.

Avelumab must be allowed to reach room temperature (15-25 °C) for minimum 30 minutes prior to use in dose preparation. Use immediately after preparation. Infusion is not intended to be stored, however, if dilution has taken place in controlled and validated aseptic conditions it may be stored for no more than 24 hours under refrigerated conditions (2-8 °C) with no more than 8 of those hours at room temperature (15-25 °C) including infusion time. If stored under refrigerated conditions, allow each bag to equilibrate to room temperature (15-25 °C), preferably for one hour before administration.

For further details and ordering, please refer to the pharmacy manual.

7.2 Treatment Schedule

Avelumab 10 mg/kg will be administered once every 14 days for a proposed duration of 8 cycles (28 day cycles), (16 doses).

If the patient is showing clinical benefit following 8 cycles of trial treatment patients may continue to receive avelumab treatment at the treating Investigator's discretion, until loss of response, toxicity, or death.

Every effort should be made for patients to attend on the scheduled visit days. However, if a patient is unable to attend on the specified day, assessments may be scheduled for +/- 3 days.

The full blood count should be assessed prior to each treatment (within 24 hours of treatment) to ensure the following criteria are met:

- Platelets $> 75 \times 10^9/L$
- Neutrophils $> 1.0 \times 10^9/L$
- Bilirubin $< 1.5 \times ULN$
- Creatinine clearance (CrCL) (Cockcroft-Gault) $\geq 30 \text{ ml/min}$.
- ALT/AST $\leq 1.5 \times ULN$ on Cycle 1 day1; thereafter $\leq 3 \times ULN$

Please also refer to Section 7.5 for dose delays and modifications, and to section 7.7 for concomitant medications.

7.3 Assessments

Table 2. Schedule of Assessments

Parameter	Screening (28 days unless otherwise stated)	Cycle 1		Cycle 2		Cycle 3		Cycle 4		Cycle 5		Cycle 6		Cycle 7		Cycle 8		Subsequent cycles		End of Treatment /Progress ion	12 month Follow- up (from treatment start)	16 month Follow- up (from treatment start)	20 month Follow- up (from treatment start)
		Day 1	Day 15	Day 1	Day 15	Day 1	Day 15	Day 1	Day 15	Day 1	Day 15	Day 1	Day 15	Day 1	Day 15	Day 1	Day 15	Day 1	Day 15				
Informed consent	X																						
Medical History	X																						
Pregnancy test (if applicable)	X	X		X		X		X		X		X		X		X		X		X			
Prior Diagnosis/ Prior Treatment / baseline conditions	X																						
ECOG performance status	X	X		X		X		X		X		X		X		X		X		X			
Height (pre-study only)	X																						
Weight	X	X		X		X		X		X		X		X		X		X					
Diagnostic tissue biopsy (within 3 months of registration)	X																			X (optional)			
Bone Marrow Trehpine biopsy (within 3 months)	X																			X ¹			
Laboratory Tests (Haematology ² and Biochemistry ³)	X ⁴	X	X	X	X	X	X ⁴	X	X	X	X	X	X	X	X	X	X	X	X ⁴				
Virology (HIV, HBV, HCV)	X																						
Urinalysis (protein, glucose)	X	X		X		X		X		X		X		X		X		X		X			

Parameter	Screening (28 days unless otherwise stated)	Cycle 1		Cycle 2		Cycle 3		Cycle 4		Cycle 5		Cycle 6		Cycle 7		Cycle 8		Subsequent cycles		End of Treatment /Progression	12 month Follow-up (from treatment start)	16 month Follow-up (from treatment start)	20 month Follow-up (from treatment start)
		Day 1	Day 15	Day 1	Day 15	Day 1	Day 15	Day 1	Day 15	Day 1	Day 15	Day 1	Day 15	Day 1	Day 15	Day 1	Day 15	Day 1	Day 15				
and blood)																							
ACTH, Thyroid function (T4 & TSH), tests for pancreatitis		X				X				X					X					X			
ECG (single 12 lead)	X	X ⁵		X ⁵																X			
Clinical Disease assessment / physical exam	X	X		X		X		X		X		X		X		X		X		X	X	X	X
CT scans with IV contrast NCAP	X					X ⁶						X ⁶				X ⁶		X ⁷	X ⁸	X	X	X	X
Avelumab 10mg/kg every 2 weeks		X	X	X	X	X	X	X	X	X	X	X	X	X	X	X	X	X					
Concomitant Diseases and Treatment		<< Ongoing assessment until 28 days after treatment discontinuation >>																					
Adverse Events		<< Ongoing assessment until 28 days after treatment discontinuation >>																					
Blood samples collected for research	X				X				X				X				X		X ⁷	X	X	X	X

1 If baseline showed involvement, a further biopsy is required at radiological CR to confirm CR. Further bone marrow biopsy should also be performed if progression within the marrow is suspected and the CT does not show progression.

2 Haematology – Full blood count (Haemoglobin, Platelets, WBC, Neutrophils and Lymphocytes)

3 Blood Chemistry – Standard blood chemistry (to include bilirubin, GGT, AST/ALT, Alkaline phosphate, Calcium (adjusted), Creatinine, CRP, Magnesium, Phosphate, Potassium, Sodium, and glucose –non fasted)

4 Triglycerides and cholesterol at baseline, Cycle 4 days 1 and End of Treatment only

5 To be performed before and after avelumab infusion

6 CT scans to be performed within the time period after the day 15 dose and prior to next day 1 dose.

7 Post 8 cycles CT scans and research bloods will be performed in line with the follow-up schedule

8 End of Treatment scan only required if treatment stopped early and no scan has been conducted in the previous 28 days. Progression scan upon suspected progression outside of scheduled scans.

7.3.1 Blood chemistry and Haematology

Full Blood count (Haemoglobin, Platelets, WBC, Neutrophils and Lymphocytes) and serum biochemistry (to include AST/ALT, Alkaline phosphate, bilirubin, Calcium (adjusted), Creatinine, Creatinine Clearance, C-Reactive Protein, Magnesium, Potassium, Sodium, GGT, Phosphate, and glucose -non fasted) will be taken within the 24h prior to each avelumab dose and at the End of Treatment visit .

Triglycerides and Cholesterol should also be assessed at Cycle 4 day 1 and End of Treatment visit only

Hormone function tests (ACTH, Free T4, and TSH) and tests for pancreatitis (such as Amylase and or Lipase as per institutional standard) will be performed prior to avelumab infusion where possible on Cycle 1 Day 1, Cycle 3 day 1, Cycle 5 day 1, Cycle 7 day 1, and at the End of treatment visit (if not performed in the previous 8 weeks). Test should additionally be performed in cases of suspected hypoadrenalism, hypopituitarism or pancreatitis.

Pregnancy test - For female patients of childbearing potential, a serum pregnancy test, with sensitivity of at least 25 mIU/mL and assayed in a certified laboratory, once at the start of screening. Urine or serum pregnancy tests will be routinely repeated at every treatment cycle during the active treatment period (immediately before investigational product administration) and at the end of study treatment visit. Additionally whenever 1 menstrual cycle is missed or when potential pregnancy is otherwise suspected this test should be repeated.

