- Active autoimmune disease that might deteriorate when receiving an immunostimulatory agent. Patients with diabetes type I, vitiligo, psoriasis, hypo- or hyperthyroid disease not requiring immunosuppressive treatment are eligible
- Known prior severe hypersensitivity to investigational product or any component in its formulations, including known severe hypersensitivity reactions to monoclonal antibodies (NCI CTCAE v4.03 Grade ≥ 3)

- Persisting toxicity related to prior therapy of Grade >1 NCI-CTCAE v 4.03; however, alopecia and sensory neuropathy Grade ≤ 2 or other Grade ≤ 2 not constituting a safety risk based on investigator's judgment are acceptable
- Pregnancy or lactation
- Known alcohol or drug abuse
- Clinically significant (i.e., active) cardiovascular disease: cerebral vascular accident/stroke (< 6 months prior to registration), myocardial infarction (< 6 months prior to registration), unstable angina, congestive heart failure (\geq New York Heart Association Classification Class II), or serious cardiac arrhythmia requiring medication
- Other severe acute or chronic medical conditions including colitis, inflammatory bowel disease, pneumonitis, pulmonary fibrosis or psychiatric conditions including recent (within the past year) or active suicidal ideation or behaviour; or laboratory abnormalities that may increase the risk associated with study participation or study treatment administration or may interfere with the interpretation of study results and, in the judgment of the investigator, would make the patient inappropriate for entry into this study
- Vaccination within 4 weeks of the first dose of avelumab and while on trial is prohibited except for administration of inactivated vaccines (e.g. the flu vaccine)
- Active infection requiring systemic therapy
- Major surgery within 4 weeks of trial entry
- Patients and partners of childbearing potential not willing to use two methods of effective contraception during and for 60 days after therapy

Trial Duration

Patients will be recruited over 24 months from 13 Trials Acceleration Programme (TAP) and non-TAP centres.

Following registration, patients will receive 8 cycles (each of 28 days duration) of avelumab (each cycle being two, fortnightly infusions of the antibody) with the possibility of continued treatment if the patient is benefitting. The patient will have an end of treatment visit within 28 days of the end of the last cycle.

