7.3.4 Physical examination/clinical disease assessment

Patients will receive a physical exam, including vital signs (blood pressure, pulse, oxygen saturation, weight and height (baseline only)), and assessment of ECOG performance status on day 1 of each cycle and at the End of Treatment visit. The physical exam should also include investigation of skin lymphoma deposits and rashes, liver and spleen assessment and assessment of lymph node measurements.

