
 • Transient (\leq 6 hours) Grade 3 flu-like symptoms or fever, which is controlled with medical management • Transient (\leq 24 hours) Grade 3 fatigue, local reactions, headache, nausea, emesis that resolves to Grade \leq 1 • Single laboratory values out of normal range that are unlikely related to study treatment according to the Investigator, do not have any clinical correlate, and resolve to Grade \leq 1 within 7 days with adequate medical management • Tumor flare phenomenon defined as local pain, irritation, or rash localized at sites of known or suspected tumor • Change in ECOG PS to \geq 3 that does not resolve to \leq 2 within 14 days (infusions should not be given on the following cycle, if the ECOG PS is \geq 3 on the day of study drug administration) • First occurrence of a Grade 3 IRR that meets conditions for continued therapy as outlined in Table 3.
Any Grade 2 AE should be managed as follows:

 • If a Grade 2 AE resolves to Grade \leq 1 by the last day of the current cycle, treatment may continue. • If a Grade 2 AE does not resolve to Grade \leq 1 by the last day of the current cycle, infusions should not be given on the following cycle. If at the end of the following cycle the event has not resolved to Grade 1, the patient should permanently discontinue treatment with a avelumab AE (except for hormone insufficiencies, that can be managed by replacement therapy; for these hormone insufficiencies, up to 2 subsequent doses may be omitted). • Upon the second occurrence of the same Grade 2 AE (except for IRR or hormone

insufficiencies that can be managed by replacement therapy) in the same patient, treatment with avelumab has to be permanently discontinued.

- Recurrent Grade 2 IRRs may not require treatment discontinuation and should be managed as outlined in Table 3

When a patient stops trial treatment an End of Treatment visit should be performed 28 days (+/- 5 days) after their last dose of avelumab. Assessments are to be performed as per section 7.3 and include:

- Physical Exam
- ECOG
- Vital signs
- Full blood count
- Biochemistry
- Hormone function
- Pregnancy test
- Urinalysis
- 12- lead ECG
- Disease assessment
- Adverse events

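### The 8-week waiver in Section 7.3.1 can accept a panel drawn before the last one to three infusions, or the pre-exposure baseline, as the End of Treatment ACTH, thyroid and pancreatitis panel

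*Combined protocol and SAP*

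**What the plan says.** Table 2 (Section 7.3) has a row for "ACTH, Thyroid function (T4 & TSH), tests for pancreatitis". It is marked at End of Treatment with no footnote and is not marked at screening. The only End of Treatment waiver among the Table 2 footnotes concerns CT scans, with a 28-day look-back.

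Section 7.3.1 says these tests "will be performed prior to avelumab infusion where possible on Cycle 1 Day 1" and on day 1 of cycles 3, 5 and 7, "and at the End of treatment visit (if not performed in the previous 8 weeks"). It adds: "Test should additionally be performed in cases of suspected hypoadrenalism, hypopituitarism or pancreatitis".

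Section 7.8 lists hormone function among the End of Treatment assessments, refers back to Section 7.3 and does not repeat the waiver. It sets the timing: "End of Treatment visit should be performed 28 days (+/- 5 days) after their last dose of avelumab". The Trial Synopsis words the timing differently: "The patient will have an end of treatment visit within 28 days of the end of the last cycle".

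Other End of Treatment checks carry no waiver. Blood count and biochemistry "will be taken within the 24h prior to each avelumab dose and at the End of Treatment visit". The physical examination and performance status are due "on day 1 of each cycle and at the End of Treatment visit".

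**The concern.** The mismatch between Table 2 and Section 7.3.1 is small on its own. A site can read the text as qualifying the table, and 8 weeks equals the spacing of the panel during treatment.

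The problem is what the waiver can accept. During treatment, a panel up to 8 weeks old is always followed by another. At End of Treatment nothing follows: Table 2 schedules no later panel. The accepted sample was normally drawn before that day's infusion, so it cannot reflect that infusion or any given afterwards. For a patient who stops after one or two doses it can be the Cycle 1 Day 1 sample, taken before any avelumab. Such a sample cannot show a treatment effect.

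Early stopping is plausible in this population. Section 7.8 requires treatment to stop at progression, and Section 1.2.3 cites a median survival of 2.5 months in primary refractory disease. Section 7.5.4 says that most immune-related reactions first appear during treatment, but also that they can be severe or fatal and can arise after avelumab is stopped. At stake is the detection of clinically silent thyroid, adrenal or pancreatic changes in patients leaving treatment. Response, survival and the primary analysis are not affected.

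**Working it through.** **Inputs**

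- Dosing every 14 days for 8 cycles of 28 days (Section 7.2). This reproduces the protocol's own count: 8 × 28 / 14 = 16 doses, on days 1, 15, ..., 211.
- Panels on day 1 of cycles 1, 3, 5 and 7 (Section 7.3.1): days 1, 57, 113 and 169, before the infusion where possible.
- Visit *v* days after the last dose, with *v* from 23 to 33 (Section 7.8).
- Waiver if the latest panel is no more than 8 × 7 = 56 days old at the visit.

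**Formula.** Let *p* be the number of infusions given since the latest panel, counting the one on the panel day (1 to 4). Then gap = 14 × (*p* − 1) + *v*.

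| *p* | Last dose number | Gap (days) | Waived? |
|---|---|---|---|
| 1 | 1, 5, 9, 13 | 23 to 33 | always |
| 2 | 2, 6, 10, 14 | 37 to 47 | always |
| 3 | 3, 7, 11, 15 | 51 to 61 | only if *v* ≤ 28 |
| 4 | 4, 8, 12 (16 is completion) | 65 to 75 | never |

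There are 15 early-stop positions (doses 1 to 15). Always waived: 4 + 4 = 8. With a visit by day 28: 8 + 4 = 12.

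**Baseline accepted.** For last doses 1 to 4 the latest scheduled panel is Cycle 1 Day 1. It is accepted after doses 1 and 2 on any permitted visit day, and after dose 3 if the visit is on days 23 to 28. That is 2 to 3 of the 15 positions.

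**Patients not affected.** Completers of exactly 16 doses have a gap of 65 to 75 days and must be tested. A patient whose last dose is dose 17 (day 225) has a gap of 225 − 169 + *v* = 79 to 89 days; later doses give longer gaps.

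**Sensitivity**

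- *One-week delay between the last panel and the last dose.* *p* = 2 becomes 44 to 54 days (waived) and *p* = 3 becomes 58 to 68 (not waived): 8 of 15.
- *Two-week delay there.* *p* = 2 becomes 51 to 61 and *p* = 3 becomes 65 to 75: 4 of 15 if *v* is 29 to 33, 8 if *v* is 23 to 28. Dose 1 has no such interval, so this kind of delay does not change it.
- *± 3 days on both panel and last dose (Section 7.2).* Dose 2 has a gap of 31 to 53 days, still waived. For *p* = 4 the minimum is 42 − 6 + 23 = 59 days, still not waived.
- *Synopsis timing (visit from the end of the last cycle to 28 days later).* A last dose in an odd cycle gives 27 to 55 days, so the same 8 positions, including doses 1 and 2, are always waived. An even cycle gives 55 to 83 days.
- *Table 2 as extracted.* The cycle 7 mark appears under day 15, which may be a PDF artefact. A panel on day 183 would change only the end of the schedule. Dose 13 would no longer be waived (169 − 113 + *v* = 79 to 89 days), doses 14 and 15 would always be waived, and 16-dose completers would have 51 to 61 days and could be waived. Doses 1 to 3 are unchanged.

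**The case against.** The strongest reply is that this is a deliberate choice with little left exposed. The look-back equals the on-treatment interval, the protocol uses a similar recency rule for CT, and Section 7.8 points to Section 7.3, so sites have a workable rule. Biochemistry at End of Treatment, including sodium, potassium, glucose, calcium and liver tests, is unconditional, as are the physical examination and adverse event review. Testing is required on suspicion, and Section 7.5.4 asks for monitoring during treatment. This stands: only unsuspected abnormalities are exposed. But the biochemistry list contains no ACTH, TSH, T4, amylase or lipase.

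Second, a silent laboratory shift would rarely reach an outcome. Under Section 8.1.1 an abnormal value counts as an adverse event only if it leads to discontinuation, dose change or intervention, or is judged clinically important, and the toxicity outcome counts grade 3 or 4 events and serious events. This also stands. The point concerns patient monitoring, not an endpoint.

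Third, the counts assume a visit on the Section 7.8 timetable. Under Table 5 an unresolved grade 2 event leads to omission of the next cycle, and permanent discontinuation may be decided only when that cycle ends. After dose 1 or 2 that is about day 56, and any visit after day 57 is more than 56 days from the Day 1 panel, so the panel would be required. Steroid tapers of at least a month under Table 4 act the same way. This narrows the group, and some patients held for possible immune toxicity would be tested. It does not help a patient who stops promptly.

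None of these points removes the case in which the rule accepts a pre-exposure sample.

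**Conclusion.** The concern holds. As written, Section 7.3.1 can accept a panel that predates the last one to three infusions. After dose 1 or 2, or dose 3 with a visit by day 28, it can accept the pre-exposure baseline, which leaves no scheduled post-exposure panel.

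On the nominal schedule the waiver covers 8 to 12 of 15 early-stop positions, and the baseline-only case covers 2 to 3 of them. This rests on the Section 7.3.1 panel dates, pre-infusion sampling (a site may occasionally draw the panel afterwards), the Section 7.8 visit window and no unscheduled panels. The documents give no distribution of stopping times, so the counts cannot be turned into a proportion of patients.

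The consequence is minor and limited to clinically unsuspected changes. The change should be made because it is cheap and removes a rule that can accept an uninformative sample, not because the risk is large.

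**What to change.** In Section 7.3.1, delete the parenthetical 8-week condition so that the text matches the unconditional mark in Table 2. Alternatively, replace it with *unless performed after the last dose of avelumab* and add a footnote to Table 2 saying so. Either version gives every patient who attends on the Section 7.8 timetable a panel drawn after the last infusion. Section 7.8 needs no change.

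The laboratory cost is at most one extra panel per patient, at a visit where blood is already drawn. The text change is one line (plus the footnote in the second version). Section 14 requires amendments to gain local approval, and the synopsis plans 13 centres, so it is sensible to carry this in the next amendment.
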